2.1.1 General definitions

Study Day

Study day will be defined as the number of days since the date of first dose of double-blind treatment. The date of first dose of double-blind treatment will be defined as Day 1 and the day before the first dose of study drug will be defined as Day -1.

Therefore, for a particular date, study day will be calculated as follows:

For dates on or after the first date of double-blind treatment,

Study day = Assessment date – Date of first dose of double-blind treatment + 1;

For dates prior to the first date of double-blind treatment,

Study day = Assessment date – Date of first dose of double-blind treatment.

In case, participant has been randomized but has not received double-blind treatment then randomization visit day will be considered as Day 1.

Baseline definition

In general, for both Part 1 and Part 2, baseline value is defined as the last measurement collected on or prior to the first dose of double-blind treatment.

Post-baseline measurement

Post-baseline values are defined as those measurements that were collected after the first dose of double-blind treatment.

When change from baseline is of interest the following formula will be used for each scheduled visit and time-point where baseline and post-baseline values are both available:

Absolute change from baseline = post-baseline value – baseline value.

Percent change from baseline = (post-baseline value – baseline value) / baseline value*100.

LDL-C to be used in analysis

The endpoints involving LDL-C will use the beta quantification (ultracentrifugation) LDL-C for all subjects. In cases where beta quantification (ultracentrifugation) LDL-C values are missing and calculated LDL-C is available, the calculated LDL-C will be used for analysis purposes.

VLDL-C

The endpoints involving VLDL-C will use the beta quantification (ultracentrifugation) VLDL-C for all subjects. In cases where beta quantification (ultracentrifugation) VLDL-C values are missing and calculated VLDL-C is available, the calculated VLDL-C will be used for analysis purposes.

Discontinuation visit mapping

For patients who discontinued the study and come to site for an early exit (EE) visit, the EE visit will be mapped to the next scheduled visit. The mapping details can be found as below:

Table 2-1 Visit mapping

Status	Last attended scheduled visit prior to EE		Mapped visit for EE	
Visit day	Visit name	Visit day	Visit name	Visit day
Discontinued (Early exit)	1	Day 1	90	Day 90
Discontinued (Early exit)	90	Day 90	150	Day 150
Discontinued (Early exit)	150	Day 150	270	Day 270

Discontinued (Early exit)	270	Day 270	330	Day 330
Discontinued (Early exit)	330	Day 330	360	Day 360
Discontinued (Early exit)	360	Day 360	450	Day 450
Discontinued (Early exit)	450	Day 450	510	Day 510
Discontinued (Early exit)	510	Day 510	630	Day 630
Discontinued (Early exit)	630	Day 630	720	Day 720
Completed			720	Day 720

2.2 Analysis sets

The Screened Set (SCR) includes all participants who provided study informed consent.

The Randomized Set (RAN) consists of all participants who received a randomization number, regardless of whether double blind treatment received or not.

The Full Analysis Set (FAS) consists of all randomized participants with the exception of those mis-randomized participants who did not receive study drug. Mis-randomized participants are defined as not qualified for randomization and were inadvertently randomized into the study. According to the intent to treat principle, participants will be analyzed according to the treatment they have been assigned to during the randomization procedure. The FAS will be used in analyses for the primary, secondary, [REDACTED] efficacy objectives in Part 1.

The Safety Set (SAF) includes all participants who received at least one dose of study treatment. Participants will be analyzed according to the study treatment received. This will be the primary population for the safety analyses in Part 1.

Note that the Safety Set allows the inclusion of non-randomized participants who receive double-blind treatment in error.

The Open-label Phase Analysis Set (OAS) includes all participants who entered in study Part 2 and received at least one dose of study treatment in Part 2. The OAS will be used to analyze the data from participants who entered Part 2.

Note that in Part 1 the number of participants in FAS equals the number of participants in SAF, so only one open-label phase analysis set is defined for Part 2.

2.2.1 Subgroup of interest

No sub-group analysis will be performed.

2.3 Disposition, demographics and other baseline characteristics

2.3.1 Disposition

The overall number of participants who entered, completed, and discontinued the study will be summarized and listed, including the reasons for discontinuation for each period: screening, Study Part 1, Study Part 2. The screening disposition will be based on SCR. The RAN will be used for the summary and listing of patient disposition for Study Part 1 and 2.

The number of participants in the FAS will be summarized by country, center, and treatment group for Part1 analysis.

Number of participants with protocol deviations will be tabulated by category (e.g., selection criteria not met, subject not withdrawn as per protocol, treatment deviation, prohibited concomitant medication, other), deviation and Part. Listing of participants with protocol deviation will be provided.

The number of participants included in each analysis set will be tabulated using SCR.

2.3.2 Demographics and other baseline characteristics

Demographic and other baseline data including age, race, gender, ethnicity, country, region (North America, Europe, Other), baseline characteristics such as body height, weight, BMI, waist circumference, smoking status, number of pack years, alcohol history, baseline disease characteristics including HoFH underlying genetic mutation(s), LDL-C, TC (total cholesterol), TG (triglycerides), PCSK9, baseline use of statins or other lipid-modifying therapies (yes, no), status of statin intolerance, baseline diabetes status as determined by fasting plasma glucose and HbA_{1C}, baseline kidney function based on eGFR, baseline SBP, DBP, pulse will be summarized descriptively by treatment group. Listings will also be provided.

Categorical data will be presented as frequencies and percentages by treatment group. For continuous data, non-missing observations, mean, standard deviation, median, 1st and 3rd quartile, minimum, and maximum will be presented. For Part 1 analysis, these data will be summarized using RAN.

No inferential statistics will be provided for baseline comparability among the treatment groups.

2.3.3 Medical history/current medical condition

Medical history will be coded with the Medical Dictionary for Regulatory Activities terminology (MedDRA) using the most recent version at the time of database lock. Medical history/conditions will be summarized by primary system organ class and preferred term, treatment group. Pre-specified solicited events selected Familial Hypercholesterolemia History and other targeted family history will be summarized separately by treatment.

For Part 1 analysis, this data will be summarized using RAN.

2.4 Treatments (study treatment, prior and concomitant therapies)

In general, all summaries of treatments of Part 1 will be performed on the SAF and all summaries of treatments of Part 2 will be performed on the OAS.

2.4.1 Study treatment

The number of study doses administered, duration on study, duration of exposure, patient year of exposure will be summarized by treatment group and Part. The analysis of exposure will also be provided for overall i.e., Part 1 and 2 data combined. Listings will be provided.

The number of participants dosed, and the injection site location will also be summarized by the study visit and treatment group.

Duration of exposure will be calculated as: minimum of (Date of last dose of treatment – Date of first dose of treatment + 180 + 1, Date of last known visit – Date of first dose of treatment + 1). For Part 1 data analysis, duration of exposure will be truncated at data cut-off date.

Patient-year of exposure will be calculated as duration of exposure/365.25.

Duration on study is defined as: date of last known visit on study – date of first dose of treatment + 1. For Part 1 data analysis, duration on study will be truncated at data cut-off date.

The patients who will discontinue the treatment prematurely before discontinuing the treatment period will be summarized by treatment group and Part, including the reason for treatment discontinuation. Listing will also be provided.

2.4.2 Prior, concomitant and post therapies

Prior (pre- baseline, defined as any medication that was stopped \geq 1 day before first dose date of study medication) medication will be summarized by treatment and concomitant (Any medication given at least once between the day of first dose of randomized study treatment and the date of the last study visit, including those which were started pre-baseline and continued into the period when study treatment is administered) medications will be summarized by treatment group and Part. Listings will be provided.

Lipid-modifying therapy (LMT) use, [REDACTED] will be summarized separately at screening and at the baseline/Randomization visit (Day 1) by treatment group using the following categories:

- Any LMT
- No LMT
- Statins
- Statins only
- Other LMT
- Other LMT only
- Ezetimibe
- Ezetimibe only

[REDACTED]

New or changed lipid-modifying therapy, [REDACTED] after baseline will be summarized by treatment group and Part.

Significant non-drug therapies prior to and after the start of the study treatment will be summarized according to the Anatomical Therapeutic Chemical (ATC) classification system and preferred term, by treatment group and Part. Significant non-drug therapies will be summarized similarly by primary system organ class, preferred term, treatment group and Part.

2.5 Analysis of the primary objective

The primary objective is to evaluate the effect of inclisiran compared to placebo on reducing LDL-C [percent change] at Day 330 (Year 1) in adolescents (aged 12 to <18 years) with HoFH and elevated LDL-C.

2.5.1 Primary endpoint

The primary endpoint i.e., primary analysis variable is the percentage change in LDL-C from the baseline measurement to the Day 330 visit.

The primary clinical question of interest is: What is the effect of the test treatment versus placebo on change in LDL-C after 330 days of treatment in adolescents with HoFH and elevated LDL-C who are on stable, optimal standard of care (SoC) lipid-lowering therapy, regardless of treatment discontinuation for any reason and regardless of unforeseen change in the concomitant lipid-lowering therapy.

The justification for the primary estimand is that it will capture both the effect of the study drug and the effect of changes in additional medication(s) used for HoFH, if they occur, as would be the case in clinical practice.

The primary estimand is described by the following attributes:

- **Population:** Adolescents with the HoFH condition of interest and elevated LDL-C on stable optimal SoC lipid-lowering therapy. Further details about the population are provided in Section 5 of the study protocol.
- **Endpoint:** Percentage change in LDL-C from baseline to Day 330 (Year 1)
- **Treatment of interest:** The randomized treatment (the investigational treatment inclisiran or the control treatment placebo) as add-on to optimal SoC lipid-lowering therapy for HoFH. The type and dose of the concomitant lipid-lowering therapy for HoFH must remain stable during Part 1 (Year 1) of the study. Further details about the investigational treatment and control treatment are provided in Section 6 of the study protocol. Data collected regardless of treatment discontinuation for any reason, regardless of unforeseen change in the concomitant lipid-lowering therapy will be used for analysis [treatment policy].
- **The summary measure:** difference between treatments in mean percentage change at Day 330.

2.5.2 Statistical hypothesis, model, and method of analysis

The primary analysis will summarize change from baseline using summary statistics to characterize change from baseline in LDL-C by treatment group and the difference between treatment groups along with 95% CI at the Day 330 time point. No formal hypothesis testing is

planned. The individual patients' data on the percentage change in LDL-C from baseline at Day 330 will be listed and depicted by waterfall plots.

2.5.3 Handling of remaining intercurrent events of primary estimands

No remaining intercurrent events are expected.

2.5.4 Handling of missing values not related to intercurrent event

The primary endpoint will not have missing data imputed. Only data from the Day 330 visit time point and baseline data needed to evaluate change from baseline in LDL-C will be included in the primary analysis.

2.5.5 Sensitivity analyses for primary endpoint/estimand

Since the sample size is small, in case of sparse data, median percentage change from baseline to Day 330 in LDL-C will be considered.

2.5.6 Supplementary analysis

A linear mixed-effects model for repeated measures (MMRM) analysis will be used as a covariate-adjusted analysis of the difference in percent change from baseline to Day 330 in LDL-C. The MMRM will include fixed effects for treatment, baseline age group ($\geq 12 < 15$ or $\geq 15 < 18$ years of age), visits, interaction between treatment and visits, and baseline LDL-C as covariates. Day 90, 150, 270, 330 and 360 will be included as visit. The Restricted Maximum Likelihood (REML) estimation approach will be used with covariance structure set as "Unstructured". If the model does not converge with unstructured covariance matrix, the compound symmetry covariance matrix will be used in the mixed model. Two-sided 95% confidence intervals for the difference between treatment groups will be provided.

The above supplementary analysis was planned but will not be performed due to the small sample size in the placebo group.

Summary statistics by treatment groups and treatment difference along with 95% CI will be provided.

2.6 Analysis of the secondary objectives

2.6.1 Secondary endpoints

Secondary efficacy endpoints include:

- Time-adjusted percent change in LDL-C from baseline after Day 90 and up to Day 330 (Year 1), defined as the average of percent changes from baseline to day 150, 270, and 330.
- Percent change and absolute change in LDL-C, Apo B, Lp(a), non-HDL-C, total cholesterol, triglycerides, HDL-C, VLDL-C, Apo A1, and PCSK9 from baseline to each assessment time up to Day 720 (Year 2)

2.6.2 Statistical hypothesis, model, and method of analysis

Descriptive summaries by treatment group will be presented for all secondary endpoints. Additionally, mean treatment difference and associated 95% CI will be provided for time-adjusted percentage change in LDL-C from baseline after Day 90 and up to Day 330, for absolute change in LDL-C at Day 330 and for percentage change in Apo B, Lp(a), non-HCL-C, total cholesterol and PCSK9 at Day 330. No formal hypothesis testing will be performed. Summaries of LDL-C by treatment, visit and subject will be additionally presented. Listings will be provided.

2.6.3 Sensitivity analyses for secondary endpoint/estimand

Since the sample size is small, in case of sparse data, median percentage change from baseline to Day 330 will be considered.

2.6.4 Supplementary analysis

Summary statistics by treatment groups and treatment difference will be provided for time-adjusted percentage change in LDL-C from baseline after Day 90 and up to Day 330 and for percentage change in Apo B, non-HCL-C, total cholesterol and PCSK9 at Day 330 and Day 720.

2.7 Safety analyses

In general, for Part 1 safety analyses, the SAF will be used; for Part 2 safety analysis, the OAS will be used.

Safety summaries will include only treatment emergent adverse events (TEAEs) by Part. For Part 1, TEAEs are adverse events (AEs) that started on or after the first dose of double-blind treatment or adverse events (AEs) that were present prior to start of double-blind treatment but increased in severity in Part 1. For Part 2, TEAEs are defined as AEs starting after the Day 360 dosing time or AEs that were present prior to the Day 360 dosing time but increased in severity in Part 2. For Part 1, if the AE start date is the same as the date of the first dose of double-blind treatment but the time is not available for comparison, the AE will be considered as treatment emergent; for Part 2, if the AE start date is the same as the date of the Day 360 treatment but the time is not available for comparison, the AE will be considered as treatment emergent

Vital signs values that have complete data and time values will be assigned to pre- or post-dose assessment (as per protocol) based on the actual date/time. For values with missing date/time, the scheduled visit date and time will be used. This rule will be applied to data from scheduled visits only. If a measurement scheduled as pre-dose is actually performed post-dose, or vice versa, the data will not be used for by visit/time point summary.

2.7.1 Adverse events (AEs)

The number (and percentage) of participants with TEAEs will be summarized by Part in the following ways:

- Overall summary.

Novartis	For business use only	Page 23
SAP amendment 4		CKJX839C12302

- By treatment, primary system organ class (SOC) and preferred term (PT).
- By treatment and PT.
- By treatment and PT for most common TEAEs (For Part 1: occurring in $\geq 15\%$ in total; for Part 2: threshold to be determined before final database lock)
- By treatment, SOC, PT, and maximum severity.
- By treatment, SOC, and PT for TEAEs leading to study drug discontinuation.
- By treatment, SOC, and PT for TEAEs related to study drug.

The number (and percentage) of participants with treatment emergent serious adverse events (TESAEs) will be summarized by Part in the following ways:

- By treatment, SOC, and PT.
- By treatment and PT.
- By treatment, SOC, and PT for TESAEs related to study drug.

Unless otherwise specified, SOCs will be sorted alphabetically and, within each SOC, the PTs will be sorted in descending order of frequency in the total column. If a participant reported more than one AE with the same PT, the AE will be counted only once. A participant with multiple AEs within a SOC is only counted once towards the total of the SOC. In case of summary by severity or relationship to study drug, summary will be done using the most severe or related occurrence respectively. Listing of all AEs and SAEs will be provided.

AE reporting for CT.gov and EudraCT

For the legal requirements of clinicaltrials.gov and EudraCT, two required tables on TEAEs which are not SAEs with an incidence greater than X% (X will be selected prior to database lock) and on TEAEs and SAEs suspected to be related to study treatment will be provided by system organ class and preferred term for on the Safety Set population.

If for a same patient, several consecutive AEs (irrespective of study treatment causality, seriousness, and severity) occurred with the same SOC and PT:

- a single occurrence will be counted if there is ≤ 1 day gap between the end date of the preceding AE and the start date of the consecutive AE.
- more than one occurrence will be counted if there is > 1 day gap between the end date of the preceding AE and the start date of the consecutive AE.

For occurrence, the presence of at least one SAE / SAE suspected to be related to study treatment / non-SAE has to be checked in a block e.g., among AEs in a ≤ 1 day gap block, if at least one SAE is occurring, then one occurrence is calculated for that SAE.

The number of deaths resulting from SAEs suspected to be related to study treatment and SAEs irrespective of study treatment relationship will be provided by SOC and PT.

These summaries will be provided after full study completion.

Injection site reactions

The number and percentage of participants who reported injection site reaction TEAEs will be summarized in the following ways:

- SOC, PT, treatment group and Part.
- SOC, PT, severity, treatment group and Part.

Listing will be provided for participants with injection site reactions.

The time to the first injection site reaction will also be summarized by treatment and Part using the following categories: $\leq 4h$, $4h$ to $\leq 12h$, $>12h$. The time (hours) to the event will be calculated from the most recent administration of study drug. The duration of the first and the longest injection site reaction will be summarized by treatment and Part using descriptive statistics. The outcome of the first and the longest injection site reaction will be summarized using the following categories: Resolved ($\leq 4h$, $>4h$ to ≤ 7 days, >7 days to ≤ 14 days, >14 days), not resolved and unknown. The total number of injection site reactions per participants will be summarized in categories (e.g., 1, 2, 3, and >3 etc.). Symptoms of injection site reactions will be summarized by treatment group and Part.

Other safety topics

The number and percentage of participants who reported TEAEs of other safety topics will be summarized by PT, treatment group and Part. PTs will be sorted in descending order of frequency in the total column. If a participant reported more than one AE within the same PT, the AE will be counted only once. If a participant reported more than one AE within the same safety topic, the participant will be counted only once at that safety topic. Listings of participants with AEs of other safety topics will be provided.

The Compound Case Retrieval Strategy (CRS) will be used to determine the MedDRA search criteria to be used to identify events of other safety topics.

AEs of other safety topics will include the following:

- Hepatic events
- Renal events
- Hypersensitivity events
- Neurological events
- Psychiatric events
- Musculoskeletal events
- Cardiac events
- New onset diabetes and worsening of glycemic control

For search criteria of AEs of other safety topics, refer to [Appendix 5.4](#).

For detailed analysis of new onset diabetes and worsening of glycemic control, please see [Section 2.7.4](#). Any immune-related events will be identified in the SOC of immune system disorders.

The percentage of participants with abnormal ECG findings reported as AEs will be summarized by treatment group and Part.

2.7.2 Deaths

Summary for deaths will be provided by SOC and PT of cause of death, treatment group, and Part. Listing of all deaths will be provided.

2.7.3 Laboratory data

Laboratory data consist of hematology, biochemistry, sexual hormones, urinalysis measurements and ADA (see [Section 2.7.6](#)). Absolute values and change from baseline will be summarized for continuous laboratory parameters by visit and box plots will also be provided by visit. Frequency table of results for categorical laboratory parameters will be presented by visit. This analysis will be performed by treatment group and Part.

Shift tables using the low, normal, high/low, or high classification (except for eGFR and HbA1c where the categories outlined below are applied) will be used to compare baseline to the worst on-treatment value by treatment group and Part. All data collected from scheduled, unscheduled and premature discontinuation visits in each part will be used to determine the worst on-treatment value.

The following categories will be used for eGFR and HbA1c:

- For eGFR, the categories will be = <30 mL/min/1.73m²; = ≥ 30 to <60 mL/min/1.73m²; = ≥ 60 to <90 mL/min/1.73m²; and = ≥90 mL/min/1.73m².
- For HbA1c, the categories will be <5.7%, ≥5.7% to <6.5%, and ≥6.5%.

The shift table dealing with the fasting plasma glucose parameter will require the lab sample to be taken fasting. Samples taken while the subjects were not fasted will not be analyzed.

For selected laboratory tests, the number and percentage of patients meeting the clinically notable criteria at any time, considering all data collected after first dose of double-blind treatment, from scheduled, unscheduled and premature discontinuation visits, will be summarized by laboratory parameter and treatment group and Part. The worst post-baseline value will be used for this analysis. Notable criteria are defined in [Appendix 5.5](#). Clinically notable criteria will be considered met when both of the following occur:

- Post-baseline value meets the clinically notable criteria.
- Baseline value does not meet the clinically notable criteria.

Furthermore, the number and percentage of participants meeting notable criteria in liver function tests (LFT) will be summarized by treatment and Part considering on-treatment data from scheduled, unscheduled and premature discontinuation visits. LFT criteria are defined in [Appendix 5.5](#).

The baseline value is the last value prior to the first dose of double-blind treatment.

All laboratory data will be listed by treatment group, participant, and visit/time and if normal ranges are available, abnormalities will be flagged.

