12.5.2 Safety endpoints

For all safety analyses, the safety set will be used. All tables will be presented by treatment group.

Safety summaries (tables, figures) include only treatment emergent events (events started after the first dose of study medication or events present prior to start of double-blind treatment but increased in severity based on preferred term) with the exception of baseline data which will also be summarized where appropriate (e.g. change from baseline summaries). In addition, a separate summary for deaths including on treatment and post treatment deaths will be provided.

In particular, summary tables for adverse events (AEs) will summarize only treatment emergent AEs.

Adverse events

The number (and percentage) of participants with treatment emergent adverse events in Part 1 and Part 2 will be summarized in the following ways:

- by treatment, primary system organ class and preferred term alphabetically.
- by treatment, primary system organ class, preferred term alphabetically and maximum severity.
- by treatment, primary system organ class and preferred term alphabetically for treatment emergent AEs leading to study drug discontinuation.
- by treatment, primary system organ class and preferred term alphabetically for treatment emergent AEs related to study drug.

The number (and percentage) of participants with treatment emergent serious adverse events in Part 1 and Part 2 will be summarized in the following ways:

- by treatment, primary system organ class and preferred term alphabetically.
- by treatment, primary system organ class and preferred term alphabetically for treatment emergent serious AEs related to study drug.

A separate summary will be provided for adverse events leading to death.

The number (and proportion) of participants with adverse events of special interest will be summarized by treatment. Categories of AEs used in this analysis will be specified in the SAP.

A participant with multiple adverse events within a primary system organ class is only counted once towards the total of the primary system organ class.

Vital signs

All vital signs data will be listed by treatment group, participant, and visit/time and if ranges are available, abnormalities (and relevant orthostatic changes) will be flagged. Summary statistics will be provided by treatment and visit/time.

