Baseline and change from baseline in height, weight, and BMI will be assessed using age- and sex-adjusted z-scores and summarized by treatment group.

Clinical laboratory evaluations

Summary statistics will be provided by treatment group and visit. Shift tables using the low, normal, or high classification will be used to compare baseline to the worst on-treatment value by treatment group for Part 1 and overall. The number (and percentage) of participants meeting clinically significant criteria will be provided by treatment group for Part 1 and overall.

Immunogenicity

ADA evaluations, including treatment emergent ADA findings, will be summarized by treatment group, participant, and visit. Additional analyses may be performed to describe the relationship between ADA and other study findings and will be detailed in the SAP.

Other safety evaluations

Baseline Tanner stage will be summarized by treatment group. Shift from baseline in Tanner stage and menarche in female participants without menarche at baseline will be summarized by treatment group.

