5.2 AEs coding/grading

The MedDRA version which will be available at the time of database lock, will be used for the coding purpose of the adverse events.

5.3 Analyses to be performed in Part 1 analysis (ANA1) and Part 2 analysis (ANA2)

	Data to be included (ANA1 and ANA2 analysis)			Comment
	Part 1	Part 2	Overall: Part 1 & Part 2 combined	
Disposition	ANA1	ANA2		
Protocol Deviations	ANA1	ANA2		
Demography and baseline characteristics	ANA1			
Medical History	ANA1			
Prior therapies (Including lipid modifying therapy)	ANA1			
Concomitant therapies**	ANA1	ANA2		SAF for ANA1;

Novartis SAP amendment 4	For business use only			Page 33 CKJX839C12302
(Including lipid modifying therapy [REDACTED])				OAS for ANA2. CM will be counted in both parts when starting from part 1 and continuing to part 2
Doses, Duration on study, Exposure	ANA1	ANA2	For exposure	
Efficacy (Primary endpoint & secondary endpoints)	ANA1			
Efficacy (secondary endpoints)	ANA1	ANA2	For some selected efficacy parameters	
AEs**	ANA1	ANA2		SAF for ANA1; OAS for ANA2.
Diabetes assessment	ANA1	ANA2		SAF for ANA1 ; OAS for ANA2.
Lab and Vital signs	ANA1	ANA2		SAF for ANA1 ; OAS for ANA2.

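### The SAP gives the protocol's combined (Parts 1 and 2) laboratory tables by Part only and moves Part 2 to a new analysis set, yet its Section 4 declares no change

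*SAP*

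**What the plan says.** **Protocol.** Section 12.5.2 sets the population without exception: "For all safety analyses, the safety set will be used". Section 12.1 defines the Safety Set as anyone with at least one dose. For laboratory data, shift tables "will be used to compare baseline to the worst on-treatment value by treatment group for Part 1 and overall", and the number of participants "meeting clinically significant criteria will be provided by treatment group for Part 1 and overall". Section 12.3 explains *overall*, for dose counts, as the two Parts combined. Section 12.5.2 does not redefine the word, and no other reading fits. Section 12.1 assigns the Full Analysis Set (FAS) to the primary and secondary objectives, and 12.5.1 runs the secondary efficacy endpoints to Day 720.

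**SAP.** In Section 2.7.3 the shift tables "will be used to compare baseline to the worst on-treatment value by treatment group and Part", and data from "visits in each part will be used to determine the worst on-treatment value". The clinically notable counts "will be summarized by laboratory parameter and treatment group and Part". The baseline is common to both Parts and is tied to the start of double-blind dosing (2.1.1): "for both Part 1 and Part 2, baseline value is defined as the last measurement collected on or prior to the first dose". Appendix 5.3 has a column for the two Parts combined. It is filled for exposure and for selected efficacy parameters, but empty in the laboratory and vital signs row. The sets in that row are the same as those in the adverse event row: "SAF for ANA1; OAS for ANA2". Section 2.2 defines this Open-label Phase Analysis Set (OAS) as participants who entered Part 2 and were dosed in it. Section 4 states that the protocol's analyses are unchanged.

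**The concern.** Long-term safety to Day 720 is a secondary objective. For the inclisiran arm, the combined laboratory table is the one that shows how many participants had a notable value at any time over two years. Two by-Part tables on a shared baseline do not supply that number, because a participant with a lasting abnormality appears once in each. The combined count could then be had only by working through the listings.

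The change of set is a separate matter. Under Protocol 9.1.1, participants who stop treatment are asked to stay and keep their visits, so a participant can have Part 2 data without a Part 2 dose. That participant belongs to the Safety Set and the FAS but not to the OAS.

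Both are departures from the protocol, and a reader who relies on Section 4 would not know of either.

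**Working it through.** **Step 1. Compare the plans.**

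| Item | Protocol | SAP |
|---|---|---|
| Shift to worst value | Part 1 and combined (12.5.2) | by Part; worst value found within each Part (2.7.3) |
| Clinically significant / notable counts | Part 1 and combined (12.5.2) | by Part (2.7.3) |
| Combined laboratory output | planned | no entry (Appendix 5.3) |
| Set for Part 2 safety | Safety Set (12.5.2) | OAS (2.2, 2.7) |
| Set for secondary efficacy to Day 720 | FAS (12.1) | FAS limited to Part 1, OAS for Part 2 data (2.2); no set named in 2.6 |
| Mixed model for LDL-C | planned (12.4.7) | cancelled (2.5.6) |
| Declared changes | – | none (Section 4) |

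The total columns in SAP 2.1 sit within the Part 1 outputs and within the Part 2 outputs, so they do not restore the combined table.

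**Step 2. Can by-Part counts stand in for the combined count?** The documents give no expected counts and the sample size rests on feasibility, so this is an illustration. About 12 participants at 2:1 gives 12 × 2/3 = 8 and 12 × 1/3 = 4. Assume that all are dosed in Part 2 and that each Part counts its own values. If *a* of *n* are notable in Part 1 and *b* in Part 2, then

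max(*a*, *b*) ≤ combined count ≤ min(*n*, *a* + *b*).

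| *n* | *a* | *b* | Combined count | Percent |
|---|---|---|---|---|
| 8 | 1 | 0 | 1 | 12.5% |
| 8 | 1 | 1 | 1 to 2 | 12.5% to 25% |
| 8 | 2 | 2 | 2 to 4 | 25% to 50% |
| 4 | 1 | 1 | 1 to 2 | 25% to 50% |

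The count is exact whenever either Part has none, or has everyone.

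**Step 3. How firm is *within each Part*?** It is explicit only for the shift table. The notable-value sentence draws on all data since the first double-blind dose, at any time, and lacks the within-Part phrase that the parallel vital signs text in 2.7.5 carries. It nevertheless ends with a split by Part. If it meant cumulative data, the Part 2 column would come close to the combined count for OAS members. The text does not settle this.

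**Step 4. Size of the set change.** Each participant followed but not dosed in Part 2 is 1/8 = 12.5% of the inclisiran arm or 1/4 = 25% of the placebo arm. The Part 2 denominator falls from 8 to 7 (one participant then weighs 14.3%, not 12.5%) or from 4 to 3 (33.3%, not 25%). At most, that person's visits at Days 450, 510, 630 and 720 leave the Part 2 tables: 4 of 9 post-baseline LDL-C visits and 4 of 10 chemistry visits. These are maxima, since 9.1.1 asks for clinic assessments after stopping only where they are possible. If everyone is dosed in Part 2, the effect is zero.

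**The case against.** The best defence is that little is hidden. The tables are descriptive, the primary endpoint is untouched, and SAP 2.7.3 lists every laboratory value by participant and visit, so with about 12 participants a combined count can be made by hand. If notable values are uncommon, one Part may well show none and the count is then exact. A set of participants dosed in Part 2 is a reasonable basis for Part 2 tables, and Protocol Section 12 leaves analysis details to the SAP. Any Part 2 injection qualifies, including the blinded Day 360 placebo given to the inclisiran arm, and 9.1.1 generally allows treatment to be restarted. The OAS may therefore leave out nobody.

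Most of this stands, and it limits the size of the point. It does not remove it: a table the protocol named should not have to be rebuilt from listings, and a reasonable change of set is still a change to declare. The reason SAP 2.2 gives, that the FAS and Safety Set are equal in number in Part 1, supports using one set in Part 2. It does not explain requiring a Part 2 dose.

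Three stronger readings are tempting, and the documents do not support them.
- *Safety data of participants who stop early are lost.* Their Part 1 events are in the Safety Set tables, later laboratory values are in the listings, and disposition uses all randomised participants. Whether the by-subject LDL-C summaries in SAP 2.6.2 include them is unclear, as no set is named there.
- *The notable table certainly counts within each Part.* Its wording is ambiguous.
- *Combined adverse event tables were dropped as well.* The protocol describes those tables for Part 1 and Part 2 and asks for no combined version.

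**Conclusion.** The point holds as a departure from the protocol that the SAP does not declare. The combined laboratory shift table and the combined count of clinically significant values are not planned in the SAP. For the shift table this is plain. For the notable counts it follows from the split by Part and the empty cell in Appendix 5.3, with the ambiguity noted. The size is modest: under assumed arms of 8 and 4, a two-year count known only to lie between, say, 2 and 4 of 8. How often such a gap would arise cannot be judged from the documents.

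The move from the Safety Set to the OAS for Part 2 safety is explicit. The move from the FAS for efficacy to Day 720 is inferred from the wording of SAP 2.2. Either affects results only if someone stopped in Part 1 and stayed in follow-up undosed, which the documents do not report. Nor is the OAS an on-drug set, since a Day 360 placebo injection is enough to enter it.

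Section 4 is incorrect on both counts, and also because SAP 2.5.6 cancels the mixed model that Protocol 12.4.7 planned.

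**What to change.** 1. Restore the laboratory shift and clinically notable tables for Parts 1 and 2 combined, on the Safety Set, by randomised group. Label the placebo-inclisiran column as mixed exposure. Add laboratory data to the combined column of Appendix 5.3. State in 2.7.3 that the by-Part notable table uses the worst value within each Part.
2. Name the FAS in SAP 2.6 for the secondary efficacy summaries to Day 720, including the combined presentation in Appendix 5.3. If an OAS version is shown as well, label it as participants dosed in Part 2, not as on drug.
3. Correct Section 4 to record, with reasons, the introduction of the OAS, any combined laboratory table that is still dropped, and the cancelled mixed model. If the sponsor keeps its present choices, this item is the minimum.

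The cost is a few tables from data already collected and some SAP wording, with no new visits or samples.
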